7.2. Discontinuation of Study Intervention

A participant will be permanently withdrawn from study treatment if any of the following symptoms or abnormalities occur, and an investigation will be carried out as described below. After withdrawal of treatment (under these conditions), where possible participants should complete the Early Withdrawal visit and be followed up for safety monitoring. Study medications will be discontinued and the participant withdrawn from the study in the event of any of the following:

[figure not shown]
- All serious infections
- Severe or serious hypersensitivity reactions, including anaphylaxis
- If the liver chemistry stopping criteria (Section 7.2.1) or QTc stopping criteria (Section 7.2.2) are met.
- Other serious or severe adverse events, at the discretion of the Investigator, after consultation with the GSK Medical Monitor.

7.2.1. Liver Chemistry Stopping Criteria

Liver chemistry stopping, and increased monitoring criteria have been designed to assure participant safety and evaluate liver event etiology.

Discontinuation of study intervention for abnormal liver tests is required when:

- a participant meets one of the conditions outlined in the algorithm.
- when in the presence of abnormal liver chemistries not meeting protocol-specified stopping rules, the investigator believes study intervention discontinuation is in the best interest of the participant.
- Study intervention will be discontinued **for a participant** if liver chemistry stopping criteria are met:

Phase 1 Liver Chemistry Stopping Criteria – Liver Stopping Event Algorithm

Abbreviations: ALT = alanine transaminase; INR = international normalized ratio; SAE = serious adverse event; ULN = upper limit of normal.

Refer to [Appendix 5](#) for required Liver Safety Actions and Follow up Assessments.

7.2.2. QTc Stopping Criteria

A subject that meets either bulleted criterion based on the average of triplicate ECG readings will be withdrawn from study intervention.

- QTcF > 500 msec,
- Increase from baseline: QTcF > 60 msec
- In this study as QTcF is used for study eligibility, thus QTcF must be used for discontinuation decisions.
- QTcF has been chosen for a participant's eligibility, the *same formula* must continue to be used for that participant *for all QTc data being collected for data analysis*. Safety ECGs and other non-protocol specified ECGs are an exception.
- If an ECG demonstrates a prolonged QTc, obtain 2 more ECGs over a brief period (see Section 8.1.3), and then use the averaged QTc values of the 3 ECGs to determine whether the subject should be discontinued from the study.
- If a clinically significant finding is identified (including, but not limited to changes from baseline in QT interval corrected using Bazett's formula [QTcB] or Fridericia's formula [QTcF]) after enrollment, the investigator or qualified designee will determine if the participant can continue in the study and if any change in participant management is needed. This review of the ECG printed at the time of collection must be documented. Any new clinically relevant finding should be reported as an AE.

7.2.3. SARS-CoV-2 related stopping criteria

If a participant develops COVID-19 like symptoms during the course of the study, procedures as specified in CHDR SOP GGECOVID will be followed.

Withdrawal of participants from the study will be at the discretion of the Principal Investigator, but should first be discussed and agreed with the GSK Medical Monitor. Further dosing and study related procedures except those required for participant safety and well being should be paused until the discussion is complete.

Participants that test positive for a SARS-CoV-2 infection after the first study dose are withdrawn from the study (after discussion with the GSK Medical Monitor and PI) will be replaced at the discretion of the Sponsor and in consultation with the Principal Investigator.

Subjects with a SARS-CoV-2 infection will be followed-up according to SOP GGECOVID.

7.3. Participant Discontinuation/Withdrawal from the Study

- A participant may withdraw from the study at any time at his/her own request or may be withdrawn at any time at the discretion of the investigator for safety, behavioural, compliance or administrative reasons. This is expected to be uncommon.
- At the time of discontinuing from the study, if possible, an early discontinuation visit should be conducted, as shown in the SoA. See SoA for data to be collected at the time of study discontinuation and follow-up and for any further evaluations that need to be completed.

- The participant will be permanently discontinued both from the study intervention and from the study at that time.
- If the participant withdraws consent for disclosure of future information, the sponsor may retain and continue to use any data collected before such a withdrawal of consent.
- If a participant withdraws from the study, he/she may request destruction of any samples taken and not tested, and the investigator must document this in the site study records.

7.4. Lost to Follow Up

A participant will be considered lost to follow-up if he or she repeatedly fails to return for scheduled visits and is unable to be contacted by the study site.

The following actions must be taken if a participant fails to return to the clinic for a required study visit:

- The site must attempt to contact the participant and reschedule the missed visit as soon as possible, counsel the participant on the importance of maintaining the assigned visit schedule and ascertain whether or not the participant wishes to and/or should continue in the study.
- Before a participant is deemed lost to follow up, the investigator or designee must make every effort to regain contact with the participant (where possible, 3 telephone calls and, if necessary, a certified letter to the participant's last known mailing address or local equivalent methods). These contact attempts should be documented in the participant's medical record.
- Should the participant continue to be unreachable, he/she will be considered to have withdrawn from the study.

Discontinuation of specific sites or of the study as a whole are handled as part of [Appendix 1](#).

8. STUDY ASSESSMENTS AND PROCEDURES

- Study procedures and their timing are summarized in the SoA.
- Protocol waivers or exemptions are not allowed.
- Immediate safety concerns should be discussed with the sponsor immediately upon occurrence or awareness to determine if the participant should continue or discontinue study intervention.
- Adherence to the study design requirements, including those specified in the SoA, is essential and required for study conduct.
- All screening evaluations must be completed and reviewed to confirm that potential participants meet all eligibility criteria. The investigator will maintain a screening

log to record details of all participants screened and to confirm eligibility or record reasons for screening failure, as applicable.

- Procedures conducted as part of the participant's routine clinical management (e.g., blood count) and obtained before signing of ICF may be utilized for screening or baseline purposes provided the procedure met the protocol-specified criteria and was performed within the time frame defined in the SoA.
 - The maximum amount of blood collected from each participant over the duration of the study, including any extra assessments that may be required, will not exceed 500 mL.
 - Repeat or unscheduled samples may be taken for safety reasons or for technical issues with the samples.

8.1. Safety Assessments

Planned time points for all safety assessments are provided in the SoA.

8.1.1. Physical Examinations

- A complete physical examination will include, at a minimum, assessments of the Skin, Cardiovascular, Respiratory, Gastrointestinal and Neurological systems. Height and weight will also be measured and recorded.
- A brief physical examination will include, at a minimum, assessments of the skin, lungs, cardiovascular system, and abdomen (liver and spleen).
- Investigators should pay special attention to clinical signs related to previous serious illnesses.

8.1.2. Vital Signs

- Tympanic body temperature, pulse rate, respiratory rate, and blood pressure will be assessed.
- Blood pressure and pulse measurements will be assessed supine with a completely automated device. Manual techniques will be used only if an automated device is not available.
- Blood pressure and pulse measurements should be preceded by at least 5 minutes of rest for the participant in a quiet setting without distractions (e.g., television, cell phones).
- Vital signs (to be taken before blood collection for laboratory tests) will consist of 1 pulse and 3 blood pressure measurements (3 consecutive blood pressure readings will be recorded at intervals of at least 1 minute). The average of the 3 blood pressure readings will be used in the analysis.

8.1.3. **Electrocardiograms**

- Triplicate or single 12-lead ECG will be obtained as outlined in the SoA (see Section 1.3) using an ECG machine that automatically calculates the heart rate and measures PR, QRS, QT, and QTc intervals. Refer to Section 7 for QTc withdrawal criteria and additional QTc readings that may be necessary.
- At each time point at which triplicate ECG are required, 3 individual ECG tracings should be obtained as closely as possible in succession, but no more than 2 minutes apart.

8.1.4. **Clinical Safety Laboratory Assessments**

- Refer to [Appendix 2](#) for the list of clinical laboratory tests to be performed and to the SoA for the timing and frequency.
- The investigator must review the laboratory report, document this review, and record any clinically relevant changes occurring during the study in the AE section of the CRF. The laboratory reports must be filed with the source documents.
- All laboratory tests with values considered clinically significantly abnormal during participation in the study after the last dose of study intervention should be repeated until the values return to normal or baseline or are no longer considered significantly abnormal by the investigator or medical monitor.
- If such values do not return to normal/baseline within a period of time judged reasonable by the investigator, the aetiology should be identified and the sponsor notified.
- All protocol-required laboratory assessments, as defined in [Appendix 2](#), must be conducted in accordance with the study reference manual or local practice and the SoA.

8.1.5. **Echocardiogram**

A transthoracic echocardiogram will be performed at screening and repeated if clinically significant changes are observed at any time during the study treatment. Images will be obtained in standard views.

8.1.6. **Skin Reactions**

Skin reactions will be recorded as Adverse Events. The investigator will assess any skin reactions for their clinical significance and clinically significant skin reactions (as per investigator's judgement) will be reviewed by a dermatologist and if appropriate a skin biopsy will be requested for histological analysis. Further technical details will be provided in the SRM.

8.2. **Adverse Events and Serious Adverse Events**

The definitions of an AE or SAE can be found in [Appendix 3](#).

AEs will be reported by the participant (or, when appropriate, by a caregiver, surrogate, or the participant's legally authorized representative).

The investigator and any qualified designees are responsible for detecting, documenting, and reporting events that meet the definition of an AE or SAE and remain responsible for following up AEs that are serious, considered related to the study intervention or the study, or that caused the participant to discontinue the study intervention (see Section 7).

8.2.1. Time Period and Frequency for Collecting AE and SAE Information

- All SAEs will be collected from the start of intervention until the follow-up visit at the time points specified in the SoA (Section 1.3). However, any SAEs assessed as related to study participation (e.g., study intervention, protocol-mandated procedures, invasive tests, or change in existing therapy) or related to a GSK product will be recorded from the time a participant consents to participate in the study.
- All AEs will be collected from the start of study intervention until the follow-up visit at the time points specified in the SoA (Section 1.3).
- Medical occurrences that begin before the start of study intervention but after obtaining informed consent will be recorded on the Medical History/Current Medical Conditions section of the case report form (CRF) not the AE section.
- All SAEs will be recorded and reported to the sponsor or designee immediately and under no circumstance should this exceed 24 hours, as indicated in [Appendix 3](#). The investigator will submit any updated SAE data to the sponsor within 24 hours of it being available.
- Investigators are not obligated to actively seek AEs or SAEs after the conclusion of the study participation. However, if the investigator learns of any SAE, including a death, at any time after a participant has been discharged from the study, and he/she considers the event to be reasonably related to the study intervention or study participation, the investigator must promptly notify the sponsor.

8.2.2. Method of Detecting AEs and SAEs

- The method of recording, evaluating, and assessing causality of AEs and SAEs and the procedures for completing and transmitting SAE reports are provided in [Appendix 3](#).
- Care will be taken not to introduce bias when detecting AE and/or SAE. Open-ended and non-leading verbal questioning of the participant is the preferred method to inquire about AE occurrence.

8.2.3. Follow-up of AEs and SAEs

After the initial AE/SAE report, the investigator is required to proactively follow each participant at subsequent visits/contacts. All SAEs will be followed until the event is resolved, stabilized, otherwise explained, or the participant is lost to follow-up (as

defined in Section 7.4). Further information on follow-up procedures is given in [Appendix 3](#).

8.2.4. Regulatory Reporting Requirements for SAEs

- Prompt notification by the investigator to the sponsor of a SAE is essential so that legal obligations and ethical responsibilities towards the safety of participants and the safety of a study intervention under clinical investigation are met.
- The sponsor has a legal responsibility to notify both the local regulatory authority and other regulatory agencies about the safety of a study intervention under clinical investigation. The sponsor will comply with country-specific regulatory requirements relating to safety reporting to the regulatory authority, Institutional Review Boards (IRB)/Independent Ethics Committees (IEC), and investigators.
- For all studies except those utilizing medical devices investigator safety reports must be prepared for suspected unexpected serious adverse reactions (SUSAR) according to local regulatory requirements and sponsor policy and forwarded to investigators as necessary.
- An investigator who receives an investigator safety report describing a SAE or other specific safety information e.g., summary or listing of SAEs) from the sponsor will review and then file it along with the Investigator's Brochure will notify the IRB/IEC, if appropriate according to local requirements.

8.2.5. Pregnancy

- Sponsor will make an effort to collect details of all pregnancies in female partners of male participants, this will be collected after the start of study intervention and until 28 weeks after the last dose.
- If a pregnancy is reported, the investigator should inform GSK within 24 hours of learning of the pregnancy and should follow the procedures outlined in [Appendix 4](#).
- Abnormal pregnancy outcomes (e.g., spontaneous abortion, fetal death, stillbirth, congenital anomalies, ectopic pregnancy) are considered SAE.

8.3. Treatment of Overdose

For this study, any dose of GSK3858279 greater than the scheduled dose will be considered an overdose. GSK does not recommend specific treatment for an overdose.

In the event of an overdose, the investigator should:

1. Contact the Medical Monitor immediately.

Closely monitor the participant for AE/SAE and laboratory abnormalities until study intervention can no longer be detected systemically (at least 56 days post-last dose of study intervention).

Document the quantity of the excess dose as well as the duration of the overdosing in the CRF.

Decisions regarding dose interruptions or modifications will be made by the investigator in consultation with the Medical Monitor based on the clinical evaluation of the participant.

8.4. Pharmacokinetics

Serum samples of approximately 3.5 mL will be collected for measurement of serum concentrations of GSK3858279 as specified in the SoA. On Day 1, each PK sample should be collected as close as possible to the planned time relative to the dose (i.e., time zero) administered to the participant on Day 1. The actual date and time of each blood sample collection will be recorded. The timing of PK samples may be altered and/or PK samples may be obtained at additional time points to ensure thorough PK monitoring, if warranted and agreed upon between the investigator and the sponsor.

Details on PK blood sample collection including processing, storage and shipping procures will be provided in the SRM.

8.4.1. Pharmacokinetic Sample Analysis

Serum (PK) analysis will be performed under the control of GSK Invitro/Invivo Translation (IVIVT). Serum concentrations of GSK3858279 will be determined using approved bioanalytical methodology. The bioanalytical site will be detailed in the relevant sample processing documents (e.g. SRM) and raw data will be archived in the GSK R&D GLP archives. Drug concentration information that may unblind the study will not be reported to investigative sites or blinded personnel until the study has been unblinded.

8.5. Pharmacodynamics

Blood samples (approximately 3.5mL) will be collected from participants in this study to investigate target engagement, with respect to the data obtained from the PainCart.

On Day 1, each PD sample should be collected as close as possible to the planned time relative to the dose (i.e., time zero) administered to the participant on Day 1. The actual date and time of each blood sample collection will be recorded. The timing of PD samples may be altered and/or PD samples may be obtained at additional time points to ensure thorough PD monitoring, if warranted and agreed upon between the investigator and the sponsor. The timing of sample collections may be adjusted based on emerging data or other new information for this study to ensure optimal evaluation of target engagement. Details of the processing, storage and shipping procedures for all samples are provided in the SRM.

All samples will be retained for a maximum of 15 years after the last participant completes the study.

8.5.1. Target Engagement

Serum samples for the evaluation of the free and total CCL17. CCL17 can be detected in circulation and is the biological target for GSK3858279. The intention is to examine the relationship between free and total CCL17 and the effect of administration of GSK3858279 on the free levels of CCL17 in the circulation.

8.5.2. PainCart

Nociceptive pain detection and tolerance thresholds can be measured using the PainCart. This is an integrated range of tests for measuring different modalities of nociception. The PainCart aims to assess as objectively as possible the levels of pain induced in human participants by a variety of potentially noxious stimuli. All measurements will be performed in a quiet room with ambient illumination and temperature. Per session, there will only be one subject in the same room. During nociceptive tasks, participants will be sitting comfortably in a designated chair, with knees supported. The order of the individual PainCart assessments will be identical for all participants and for all time-points. See [Appendix 7](#) for further details.

8.6. Genetics

Genetics are not evaluated in this study.

8.7. Biomarkers

Biomarkers are not planned to be evaluated in this study.

8.8. Immunogenicity Assessments

Serum samples (approximately 5 mL) will be collected from all treated participants at pre-dose and various time points post-dosing, see SoA. Testing will be performed using the typical tiered approach involving screening, confirmation and titration assays [EMEA, 2017; FDA, 2014], performed by Clinical Immunology, GlaxoSmithKline. If sera contain potential anti-GSK3858279 antibodies, they will be confirmed by immune-competition using excess drug, followed by a titration assay. Results will include the incidence of immunogenicity, antibody specificity and titres.

For each participant, immunogenicity results, including the incidence and titres, will be reported.

8.9. Health Economics

Health Economics parameters are not evaluated in this study.

9. STATISTICAL CONSIDERATIONS

9.1. Statistical Hypotheses

The study will test the null hypothesis that there is no difference between GSK3858279 and placebo versus the alternative hypothesis that GSK3858279 is superior from placebo on the endpoints described: UVB heat pain detection test, cold pressor time to intolerable pain threshold test and electrical pain tolerance threshold test in the PainCart scale. No Adjustment will be made for multiplicity.

9.2. Sample Size Determination

A maximum of 30 participants will be randomized into the study as per Section 6.3.1 such that approximately 24 participants complete all three periods of the study (except UVB assessments on irradiated skin). Approximately 18 subjects will undergo the UVB assessments on irradiated skin such that approximately 15 subjects complete the UVB assessments in all three periods.

On each of the three endpoints, a positive conclusion will be declared if, given the data, there is at least 90% probability that the ratio vs placebo is better than 1 (no difference) and a negative conclusion will be declared if, given the data, there is less than 75% probability that the difference vs placebo is better than 1 (no difference).

The coefficient of variation for each endpoint was estimated from [Loudon, 2018](#); [Okkerse, 2017](#); [Siebenga, 2019](#); [van Amerongen, 2018](#), and is shown in [Table 1](#).

Table 1 Coefficient of Variability

UVB heat pain detection (°C)	Cold pressor time to intolerable pain threshold (sec)	Electrical pain tolerance threshold (mA)
3.7%	25.6%	19.1%

With 24 completed participants using a three-period two-treatment incomplete-block crossover design, the probability of declaring a positive outcome on each endpoint where there is no improvement is fixed at 10% by definition (Type I Error). The operating characteristics of each endpoint is provided in [Figure 4](#).

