9.2.1. Sample Size Sensitivity

The impact of increases/decreases in the variability of each endpoint from the expected variability is demonstrated in [Figure 4](#) and [Figure 5](#). Subject drop out of 20% is accounted for in the sample size. Operating characteristics and probability of positive outcomes [Figure 4](#) and [Figure 5](#) are based on a sample size of 24 for Electrical pain tolerance and Cold pressor time to intolerable pain threshold, and sample size of 15 for UVB heat pain detection on irradiated skin.

Figure 4 Operating Characteristics of Study Design. a: Electrical pain tolerance threshold (mA) b: Cold pressor time to intolerable pain threshold (sec) c: UVB heat pain detection ($^{\circ}\text{C}$)

[figure not shown]
[figure not shown]

Figure 5 Probability of positive conclusion based on different assumptions.
a: Electrical pain tolerance threshold (mA) **b:** Cold pressor time to intolerable pain threshold (sec) : UVB heat pain detection (°C)

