10.7.1.1.1. Thermal pain

Thermal pain detection and tolerance thresholds are determined using the Q-sense (Medoc, Israel), which controls a 30 x 30 mm thermode that is placed on the subjects

back. The initial temperature of the thermode will be 32°C and will increase by $0.5^{\circ}\text{C}\cdot\text{s}^{-1}$ until the subject perceives the stimulus as painful (Pain Detection Threshold [PDT] - indicated with pushing a button on a hand-held feedback control) or when a temperature of 50°C is reached. The average of a triplicate measurement will be used to determine pain thresholds.

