
 The MCMC iterations are flagged if the posterior summary ratio > X, where X is various criteria. The posterior probability is then calculated by summarising the number of flagged MCMC iterations / total number of MCMC iterations.
Model Checking & Diagnostics

 Refer to the relevant documentation (Bayesian Statistics Best Practice at GSK – Clinical Trials using Bayesian Inference).
Model Results Presentation

 The posterior ratio to baseline AAUC median for each treatment group will be presented along with the coefficient of variation (CV) (%) (calculated as $\sqrt{\exp(sd^2) - 1}$) and/or 95% credible intervals (Crl). The posterior treatment ratio to placebo, along with corresponding 95% Credible Intervals (Crl) and posterior probabilities that the true ratio is greater than 1 will be presented. If the Ratio to Baseline is not suitable, the change from baseline AAUC in UVB heat pain detection will be compared between the treatment groups using a Bayesian mixed ANCOVA with the same model specification as above. All available post-baseline scheduled visits will be included in the analysis. Non-informative priors will be used for all modelling parameters. Wherever possible conjugate priors will be utilised. An unstructured covariance matrix will be used to model the within-subject error.

7.1.5.1.2. Cold pressor time to intolerable pain & Electrical pain tolerance threshold – single stimulus

Endpoint / Variables

 Ratio to baseline in cold pressor time to intolerable pain threshold (seconds) (AAUC 1-15 days) Ratio to baseline in electrical pain tolerance threshold (mA) – single stimulus (AAUC 1-15 days) If ratio to baseline is deemed suitable due to the distribution of the parameters, the response will be log transformed. Any transformation of a response variable is also expected to be applied to the corresponding baseline variable. Final decisions on transformations will be based on the observed data and model diagnostics
Model Specification

 A Bayesian mixed ANCOVA model will be fitted to the ratio to baseline AAUC (1-15 days) for the electrical pain tolerance threshold endpoint and cold pressor time to intolerable pain endpoint, and used to estimate the ratio to placebo. Refer to Section 7.1.5.1.1 Model Specification for more information
Model Checking & Diagnostics

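### Protocol 9.2 sets the positive rule on the ratio to placebo but the negative rule on the difference, both against 1, so read literally the two conclusions can overlap

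*Protocol*

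**What the plan says.** Protocol 9.2 gives both decision rules in one sentence, and they apply to each of the three primary endpoints.

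- Positive: "there is at least 90% probability that the ratio vs placebo is better than 1 (no difference".
- Negative: "there is less than 75% probability that the difference vs placebo is better than 1 (no difference".

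The same section then says that "the probability of declaring a positive outcome on each endpoint where there is no improvement is fixed at 10% by definition (Type I Error".

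Protocol 9.4.2 plans a model on change from baseline. SAP 7.1.2 analyses log change from baseline, back-transformed to a ratio. For the results, SAP 7.1.5.1.1 says that "posterior probabilities that the true ratio is greater than 1 will be presented". It leaves the threshold for flagging posterior draws as an unspecified X. SAP 2.4 and 7.1.5.1.1 keep change from baseline as a fallback if the ratio is unsuitable.

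The 90% and 75% cut-offs do not appear in the SAP. SAP Table 1 records a change to Protocol 9.1 but none to 9.2.

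**The concern.** The two rules share the benchmark 1 and the same gloss that 1 means no effect. That gloss is true of a ratio and false of a difference. On the raw scales a difference of 1 is 1 °C, 1 second or 1 mA.

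A rule with cut-offs at 90% and 75% should produce three separate outcomes: positive, negative, and inconclusive in between. That works only if both cut-offs apply to the same posterior probability. If one applies to the ratio and the other to a raw difference of 1, a single result can satisfy both. The raw scale also occurs in the plan, through Protocol 9.4.2 and the SAP fallback. What is at stake is whether the reported conclusion for each endpoint follows unambiguously from the data.

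**Working it through.** **Inputs from the documents.** The CVs are 3.7% (UVB), 25.6% (cold pressor) and 19.1% (electrical), from Protocol Table 1. Protocol 9.2.1 uses a "sample size of 15 for UVB heat pain detection on irradiated skin" and 24 for the other two endpoints. The sequences are A/P/P and P/A/A (SAP 5.1).

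**Assumptions.** The CVs are within-participant, which the documents do not state. The prior is flat and the posterior approximately normal. The treatment-by-period term, baseline covariates and AAUC averaging are ignored. No mean UVB threshold is given, so 40 °C is assumed. The range shown is 32 to 50 °C, the thermode limits in Protocol 10.7.1.1.1 ("The initial temperature of the thermode will be 32" °C, stopping "when a temperature of 50" °C is reached).

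**1. The plan's own figure.** At a true ratio of 1, the chance that the posterior probability reaches 90% is 1 − Φ(1.2816) = 10%. The stated Type I error is reproduced and does not depend on the negative rule.

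**2. Standard error.** For A/P/P, the treatment indicator centred within participant is (2/3, −1/3, −1/3). Its squares sum to 2/3, and P/A/A gives the same. The variance is therefore 1.5σ²/n. For UVB, σ = √ln(1 + 0.037²) = 0.0370, and SE = 0.0370 × √(1.5/15) = 0.0117 on the log scale. In °C it is about 0.0117 × mean.

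**3. Both rules on the ratio.**
- Positive if the estimated ratio is at least exp(1.2816 × 0.0117) = 1.0151.
- Negative if it is below exp(0.6745 × 0.0117) = 1.0079.
- Inconclusive in between.

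At a true ratio of 1 these outcomes have probabilities of 10%, 75% and 15%, and they cannot overlap.

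**4. The rules as written, UVB.** Positive if the estimate is at least 1.2816 × SE. Literally negative if it is below 1 + 0.6745 × SE, in °C.

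| Assumed mean | SE (°C) | Positive from | Literal negative below | Both met, true effect +1 °C | Both met, no effect |
|---|---|---|---|---|---|
| 32 °C | 0.374 | +0.48 | +1.25 | 67% | 10% |
| 40 °C | 0.468 | +0.60 | +1.32 | 55% | 10% |
| 50 °C | 0.585 | +0.75 | +1.39 | 42% | 9% |

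At 40 °C the overlap runs from +0.30 to +1.16 °C if the CV is halved, and from +1.20 to +1.63 °C if it is doubled.

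As an example, an estimated ratio of 1.02 gives P(ratio > 1) = Φ(0.0198/0.0117) = 95.5%, which is positive. At 40 °C the same result is +0.8 °C, and P(difference > 1 °C) = 1 − Φ(0.2/0.468) = 33%, which is literally negative.

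**5. The other endpoints.** Overlap needs 1.2816 × SE < 1 + 0.6745 × SE, so the mean must be below 1/(0.6071 × SE of the log ratio).
- Cold pressor: SE = 0.0630, so the mean must be below about 26 s.
- Electrical: SE = 0.0473, so the mean must be below about 35 mA.
- UVB: the limit is about 141 °C, far above the thermode maximum.

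**6. A difference of ratios.** If *difference* meant one ratio to baseline minus another, exceeding 1 would be practically impossible. Every result would then be negative, including every positive one.

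**The case against.** The strongest reply is that this is a slip which the sentence itself resolves. Both clauses gloss 1 as no effect, and that fits only a ratio. The documents also use *difference* loosely for any treatment contrast: SAP 2.4 speaks of estimating a difference and then lists three ratio-to-baseline endpoints. The primary SAP analysis computes the probability that the true ratio exceeds 1 and defines no probability of exceeding 1 °C. A contradictory result would need a posterior quantity that nobody has planned. All of this stands, and it settles what was meant. It does not correct the rule, because no supplied section repeats the cut-offs on the intended scale.

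It is also fair that the percentages at a true +1 °C effect depend on a chosen effect size and assumed means. They show that the overlap is not a marginal case, and no more than that.

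A reader might infer that a drug with no effect would generally be called negative far more often than the intended 75%. For UVB the literal rate is indeed at least 99% over 32 to 50 °C. For cold pressor at an assumed 60 s, however, the SE is 0.0630 × 60 = 3.78 s, and Φ(1/3.78 + 0.6745) = 83%. The general statement is not supported.

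**Conclusion.** Protocol 9.2 is wrong as written, almost certainly through one misplaced word. It is the only statement of the positive and negative rules in the supplied documents, and taken literally it allows one result to meet both. For UVB the overlap is about +0.6 to +1.3 °C at an assumed 40 °C mean with a within-participant CV of 3.7% and 15 completers. It persists across the thermode range and with the CV halved or doubled. For cold pressor and electrical pain it depends on the unstated mean.

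Two stronger readings should be resisted. A reader might infer that the design or its error rate is faulty, but the 10% Type I error reproduces and is untouched. A reader might also infer that the literal rule drove the futility termination recorded in SAP 1.1. Nothing in the documents shows that it was used. The futility criteria are referred to the interim charter, which was not supplied and may state the rule correctly.

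The point is therefore a correction to a stated decision rule. Its value lies in unambiguous reporting, since the study has already stopped.

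**What to change.** 1. In the negative rule of Protocol 9.2, change *difference* to *ratio*.
2. In SAP 7.1.5.1.1, restate both rules on one quantity: positive if P(ratio > 1) is at least 90%, negative if it is below 75%, inconclusive otherwise. SAP 7.1.5.1.2 refers back to that section, so cold pressor and electrical pain are covered.
3. In the same place, state that if the change-from-baseline fallback is used, both cut-offs apply to P(difference > 0). Changing the protocol word alone would leave the fallback without a rule.
4. If the protocol can no longer be amended, record the correction in SAP Table 1 as a change to Protocol 9.2.

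The cost is one word in the protocol and a short paragraph in the SAP. The primary analysis already yields P(ratio > 1), so no new analysis is needed. The fallback probability would come from the fallback model's own posterior draws.
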